5.2 Handling of Study Interventions

Three methods of mindfulness meditation will be taught, consisting of: 1) the body scan; 2) sitting practice/awareness of breathing; 3) mindful movement/yoga. An instructor manual has been created to guide the providers at all three HCS sites.

5.3 Concomitant Interventions

5.3.1 Allowed Interventions

OPTIMUM medical group mindfulness clinical pain program.

5.3.2 Required Interventions

None.

5.3.3 Prohibited Interventions

None.

5.4 Adherence Assessment

Assessment and monitoring: Attendance at group sessions will be obtained through the EHR (registered appointment) as patients will need to check in as a telehealth visit and that check-in is logged into the EHR. Unblinded study staff will record attendance. Adherence-promoting strategies include providing guided meditation recordings and instructional materials. Group sessions will stress the importance of home practice and group participation, and discussion will include problem-solving around barriers to the meditation practice and coping with pain.

Treatment fidelity and credibility: The mindfulness instructors will meet weekly during the first 6-months of the UH3 phase of the trial along with [name], [name], and [name] to discuss the delivery of the program in primary care through a telehealth video format, review the structure and format of the sessions, and troubleshoot barriers as they arise. After the first 6-months meetings will be biweekly and starting in Year 2 of the UH3 will be monthly. More frequent or less frequent meetings will be at the discretion of the group. It is critical during this demonstration project to meet regularly to address issues of program delivery and integration into clinic. Additionally, [name] has been trained in the use of the Mindfulness-based Interventions-Teaching Assessment Criteria (MBI-TAC), a standardized system for rating competency of mindfulness instructors and she will be able to provide guidance on evaluating treatment fidelity in a pragmatic setting. Training and monitoring at the three HCS sites will consist of: 1) a combined 3-hour online MGV training led by the respective site PIs and facilitated by [name]; 2) weekly to monthly meetings, as noted above; and 3) facilitator evaluation and group fidelity monitoring, led by [name].

6. STUDY PROCEDURES

6.1 Schedule of Evaluations (Table 1)

Assessment	Screening & Consent	Baseline (T1)	OPTIMUM Program 1-8 weeks, End of 8 weeks (T2)	Monthly Pain Medication and Healthcare Encounters	Follow-up after 6 months (T3)	Follow-up months (T4)
Informed Consent Form	X					
Demographics		X				
Screening Questionnaire	X					
Inclusion/Exclusion Criteria	X					
Enrollment/Randomization	X					
Adverse Events			X		X	
Study Measures		X	X	X	X	

6.2 Description of Evaluations

6.2.1 Screening Evaluation

Procedures to determine whether a potential participant is eligible to take part in the trial are known as screening procedures.

Consenting Procedure

We have requested and received IRB approval for a waiver of the requirement to obtain a signed, written informed consent for the preliminary screening procedures used to determine the eligibility of potential participants. Screening will occur over the phone and an IRB approved script will be used, followed by the screening questionnaire.

In person screening: After the COVID pandemic, in-person screening procedures may occur since potential participants can be identified before their visit through medical record review. When potentially eligible patients are identified before their upcoming in person office visit

because they have a low back pain diagnosis, they will be approached ONLY if their provider agrees. They will be asked if they would be interested in hearing about the study, some brief eligibility questions and if they are eligible, would they like to hear more about the study. This will count as verbal consent (IRB approved script will be followed) for the preliminary screening procedure. Since, the screening procedures consist only of the basic information from interested potential participants, we believe it is conventional to defer obtaining written informed consent.

Informed consent: We have obtained IRB permission to obtain verbal informed consent, obtained through a telephone interview. After the screening procedure, eligible participants will be provided with a copy of informed consent through email. All will be encouraged to review the consent form before undergoing informed consent. A listed investigator or designated study team member trained in informed consent will obtain informed consent from each study participant before the start of any research/intervention procedures. A page-by-page review of the consent form will occur and the potential study subject will be asked for a verbal indication of their understanding of the material contained in the consent form. They will also be asked if they have any questions. Participants will then be asked to verbally consent, if they agree with the material and wish to be enrolled in the study. The potential participants may reschedule their enrollment visit should they feel that they need more time to decide about enrollment.

We will also administer an electronic informed consent for subjects who wish to complete the procedure online and not over the telephone.

Screening

Screening will be established by telephone. Participants will undergo screening if they are identified in EPIC (Electronic Health Record System) or they self-refer as a result of having heard about the trial from the HCS sites research registry, clinician referral or posted flyers or if they receive a letter from their provider to participate in the study. Recruitment will also occur by using the Clinical Data Warehouse at Boston Medical Center that allows for identifying patients with a diagnosis of low back pain. At the University of Pittsburgh a similar process is available through the University of Pittsburgh CTSI. Additionally, all sites may use research registries to identify subjects. Screening includes questions designed to inform potential participants about the study and help the study team in determining whether he/she is initially eligible. This procedure takes approximately 6-10 minutes to complete.

Potential participants will be informed about the eligibility during the screening procedure.

Because the intervention is delivered in cohorts, if there has been more than an 8-week delay between screening and the start of the cohort, then the participant will be rescreened for eligibility with the PEG. If the score is < 3 they will be ineligible.

6.2.2 Enrollment, Baseline, and/or Randomization

Enrollment

Enrollment in the trials refers to the stage when participant is completely eligible, has given informed consent, completed the required screening and demographics and has been randomized. Randomization will occur after the baseline assessment.

Baseline Assessments and Study Measures

Once informed consent has been obtained and eligibility confirmed baseline measures will be completed. The baseline and subsequent assessments (T1-T4 and monthly assessments) will be completed electronically or over the telephone, per patient preference. We will also mail the measures to patients if that is the only way they will complete the measures. A self-addressed, stamped envelope will be included.

Assessing improvement in a patient's chronic pain condition is challenging because unlike diabetes, hypertension, or obesity there is not yet bloodwork or objective measurements that can be easily ordered or obtained. PCPs thus rely on self-report of improvement that may or may not involve a scale. The CDC's guidelines for the prescription of opioids for chronic pain provide recommendations for pain evaluation and treatment that inform our outcomes. The CDC guidelines include evaluating the multidimensional impact of chronic pain with validated scales that measure pain intensity, function (in its broader sense to include physical, emotional and social function or quality of life), mood, sleep, pain catastrophizing, and anxiety.⁵⁹ Additionally, they reiterate that a 30% improvement in pain and function is clinically meaningful. A recent comprehensive review of measures to include in chronic pain trials recommended the PEG composite score, PROMIS 4-item function (obtained from the PROMIS 29) and scales for evaluating mood, anxiety, and global impression of change. To evaluate the association between pain and trauma, we have added the Life Events Checklist for DSM-5 (LEC-5). We have followed these recommendations for the patient-reported outcomes (PRO) measures as shown in Table 3. Given these recommendations, as well as the well-established use of the PEG composite score in clinical practice and its low patient burden we will use the PEG composite score as the primary outcome measure. Because administering these measures is not part of usual care, except for the PEG composite score, we will capture PROs directly from patients during four key time points of the PCT.

We will obtain healthcare resource utilization directly from the EHR (Table 3). The EHR will evaluate opioids according to prescriptions written; CT/MRIs performed; invasive procedures such as injections and surgeries; outpatient primary care visits, physical therapy visits, urgent care visits, ED visits, and hospitalizations. Most utilization outcomes will be treated as count data and cumulative opioid exposure as continuous (i.e., cumulative morphine equivalents).

All 450 participants who are included based upon the screening criteria outlined above will receive identical assessments. We will use a paperless data management system that is described below. The measures are quick to administer and complete. In our experience, almost all the individual measures can be done in 5 minutes or less. The total time for assessment is expected to be 20 minutes, with many people completing measures in less time.

We will also conduct an online survey with all PCPs in the participating practice, to learn about their perspectives on how well the study procedures integrated with their work flow, overcame common barriers to chronic pain management, and were consistent with the practice's typical referral and feedback protocols. This survey will also ask PCPs to report if/how many of their patients enrolled raised safety concerns during the study, overall satisfaction with the program, and open-ended questions will solicit feedback for protocol improvements.

Outcome Measures Table (Table 2)

	T1 Baseline	T2 8-wks	*T3 6-mo	T4 12-mo	Number of Questions
Patient-reported Measures					
**PEG	X	X	X	X	3
PROMIS-29 (Q.1-4 & 17-20 same as PROMIS Physical Function & PROMIS Sleep	X	X	X	X	29
Current Opioid Misuse Measure	X	X	X	X	17
CAMS-R (mindfulness)	X	X	X	X	12
Satisfaction, single item		X	X	X	1
Ethics, single item		X			1
Patient Global Impression of Change PGIC		X	X	X	1
Opioid Use, single item	X	X	X	X	1
Pain Catastrophizing Scale Short Form	X	X	X	X	6
Demographics	X				~23
Tobacco, Alcohol, Prescription medications, and other Substance (TAPS).	X			X	5
Screening questionnaire	X				~10
Pain Medication (s) This form will be asked monthly	X	X	X	X	
Charlson Co-Morbidity Index	X				23

Health Care System Utilization (self-report). This form will be asked monthly		X	X	X	~20
HEAL-Expectation	X				6
Telehealth Usability Questionnaire	X	X			7
Total Questions OPTIMUM					(baseline) (other time points)
Life Events Checklist for DSM-5 (LEC-5), *This form will be asked once at any upcoming timepoint (including monthly assessments)		*	*	*	17
Global Mindfulness				X	13
EHR Outcomes					
Opioid prescriptions and other prescriptions for pain, CT/MRIs of lumbar-sacral spine, injections of lumbar-sacral spine, ED/urgent care visits for LBP, Surgeries of lumbar spine, hospitalizations for LBP, PCP visits for LBP, physical therapy referrals for LBP	X		X		X
Core HEAL Pain Data Measures					
PROMIS Physical Function (questions 1-4 same as in PROMIS 29 questions 1-4)	X		X		2 additional questions
PROMIS Sleep (questions 1-4 same as in PROMIS 29 questions 17-20)	X		X		2 additional questions
Sleep Disturbance	X		X		2
Depression PHQ-2	X		X		2
Anxiety GAD-2	X		X		2

*Primary Timepoint **Primary outcome.

Pain impact is defined as Pain intensity, pain interference and functional status calculated from 9 items of the PROMIS-29. PROMIS: patient reported outcomes measurement information system.

Yellow Highlight=Core HEAL Measures incorporating into OPTIMUM outcomes.

Additional Baseline Variables: We will assess age, sex, race, ethnicity, and socioeconomic status, involvement in workers' compensation, work status, previous treatment including nonpharmacological therapies, and marital and educational status. Biomedical factors will include: a) comorbidity: data on comorbidity will be gathered using the Charlson Co-Morbidity Index T1;⁶⁰ b) pain medications (regularly scheduled and as-needed) at T1-T4 and will be categorized into sub-classes: i) salicylates (aspirin > 1200 mg/day, salsalate); ii) non-aspirin, non-COX2 selective NSAIDs; ii) COX2 selective NSAIDs; iv) acetaminophen; v) opioids; vi) skeletal muscle relaxants; vii) adjunctive agents (e.g., corticosteroids, capsaicin, Neurontin); and c) antidepressants and antianxiety medications. Regularly scheduled opioid analgesics will be converted to daily oral morphine equivalents.⁶¹

Randomization

To ensure balance between groups, we will use permuted block randomization with block size of 4 or 6, in a 1:1 ratio, stratified by clinic and sex. Participants will be randomized after completion of baseline measures.

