9.5 Outcomes

9.5.1 Primary Outcome

The PEG composite score is the primary outcome measure. This will be used to measure the pain intensity, interference, and enjoyment. Six months (T3) will be the primary time point.

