The table below is of power calculations for the Optimum study using the PEG as the primary outcome. An ICC estimate of 0.053 was used, which came from [name] pragmatic clinical trial funded by NINDS which used the PEG. The other assumptions are $\alpha = 0.05$, SD of change = 2.5 and 20% attrition. As the table illustrates, with a total sample size of 450, with an average of 10 subjects per cluster, we have close to 90% power to detect a 1-unit difference in the PEG between groups. The table also illustrates calculations for a range of power and effect sizes.

ICC = 0.053

Obs	power	meandiff	SD	clustsize	final_npergroup
1	0.80	1.0	2.5	10	184.625
2	0.85	1.0	2.5	10	210.473
3	0.90	1.0	2.5	10	245.551
4	0.80	1.5	2.5	10	83.081
5	0.85	1.5	2.5	10	94.159
6	0.90	1.5	2.5	10	110.775
7	0.80	2.0	2.5	10	48.003
8	0.85	2.0	2.5	10	55.388
9	0.90	2.0	2.5	10	62.773
10	0.80	2.5	2.5	10	31.386
11	0.85	2.5	2.5	10	35.079
12	0.90	2.5	2.5	10	42.464
13	0.80	3.0	2.5	10	22.155

Obs	power	meandiff	SD	clustsize	final_npergroup
14	0.85	3.0	2.5	10	25.848
15	0.90	3.0	2.5	10	29.540

Missing Data Considerations:

We anticipate 20% attrition at the 8-week time point. We chose a higher attrition rate than in our previous work as we anticipate more attrition in the PCT as patients will not have the “high touch” of participants in the RCTs.^{5, 26, 28} Our sample size analyses have accounted for this amount of missing data. We will compare baseline characteristics between patients with the assessment immediately following the 8-week program to those without in order to assess potential bias in study completion. We will also try to obtain reasons for study drop out so that we can assess the missing data mechanism (missing completely at random (MCAR), missing at random (MAR), non-ignorable missingness). At a single time point, we will conduct sensitivity analyses assigning poor scores and good scores for missing values differentially by treatment assignment to evaluate the impact on our study results.

The mixed models proposed for analysis are robust to missing data under MCAR and MAR missing data mechanisms. If the amount missing data differs between treatment groups or appears to be non-ignorably missing, we will conduct sensitivity analyses with imputed data based on varying assumptions (ignorable vs. non-ignorable missingness).

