10.2 Data Management

EHR Data: Consenting and eligible participants will provide contact information containing protected health information (PHI) to each HCS’s research staff. PHI will be stored separately from clinical data in a password protected electronic file and will be used to link and extract clinical data from each center’s EHR on a bi-weekly basis. Limited use datasets will be created

at each HCS and will contain a unique study identifier and clinical data including date of birth and visit dates; name, address, social security number and medical record number information will be removed. Limited use datasets will be transferred to the central data repository housed at Boston University Biostatistics and Epidemiology Data Analytics Center (BEDAC). The BEDAC is supported by the Boston University Medical Campus (BUMC) Information Systems and Technology group (IS&T). Data will reside on virtual machines stored inside the BUMC IS&T premium secure environment. Under IS&T, project database access is configured to require encrypted connections, databases are encrypted at rest (AES-256), and all actions to the database are logged. Database transfer will be electronically encrypted via IPsec tunnel or secure socket layering (SSL) encryption technology so that only the intended recipient can decode the data. Applications and databases will be protected by network firewalls that restrict access to designated users and hosts. Restriction and permissions to update the database and to share the database will be controlled by the BEDAC based on staff user role. The BEDAC data manager will develop data transfer specifications and work with each HCS to obtain data through the secure BEDAC portal. The limited use EHR data will be cleaned, aggregated and merged with study data for subsequent analysis.

Missing data: We do not expect substantial missing data due to it being directly entered into the electronic data collection system, which we have used previously. This system has many safeguards such as prohibiting closure of a page if a question has not been answered or the answer is out of range. For instruments with several questions we will use the approach recommended by their authors for calculating total scores and composites when values for an item are missing.

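### No PEG-only fallback is specified for participants who do not complete the T3 assessment, and PEG scores recorded in usual care are not addressed

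*Combined protocol and SAP*

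**What the plan says.** Section 9.5.1 names the PEG as the primary outcome and adds: "Six months (T3) will be the primary time point". Section 6.2.2 chooses the PEG partly because it burdens patients little.

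The PEG is given with the other self-report measures, electronically or by telephone. As a last resort: "We will also mail the measures to patients if that is the only way they will complete the measures". All 450 participants are to receive the same assessments, and "The total time for assessment is expected to be 20 minutes", with many expected to need less. Sections 6.2.2 and 9.6 give no order of administration, no minimum data set and no contact limited to the PEG.

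On usual care, Section 6.2.2 says: "Because administering these measures is not part of usual care, except for the PEG composite score, we will capture PROs directly from patients". The same paragraph says: "PCPs thus rely on self-report of improvement that may or may not involve a scale". Section 10.2 has clinical data extracted from each center's "EHR on a bi-weekly basis". The EHR rows of Table 2 begin "Opioid prescriptions and other prescriptions for pain, CT/MRIs of lumbar-sacral spine" and go on to other utilization items. No PEG score is listed.

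Section 9.6 says: "We anticipate 20% attrition at the 8-week time point". It plans mixed models that rely on data missing at random, a sensitivity analysis assigning good and poor scores differentially by arm, and imputation under ignorable and non-ignorable assumptions. Section 10.3.3 aims for at least 85% follow-up at every time point.

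**The concern.** Three questions carry the primary result, but the plan describes them only as part of a much longer set. Someone unwilling to give about 20 minutes at T3 might still answer three questions by telephone, and the plan has no step that asks. Where such a person gives nothing, the T3 value is left to the model or to assigned scores.

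Participants know their arm and rate their own pain, so non-response at T3 could depend on both. The missing-at-random assumption cannot be checked from the observed data, and each observed value reduces the weight placed on it. The plan also describes the PEG as belonging to usual care and already extracts EHR data, but does not say whether chart scores have any role.

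**Working it through.** **1. Items at T3 (Table 2, Section 6.2.2)**

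| Block | Items |
|---|---|
| PEG 3, PROMIS-29 29, Current Opioid Misuse Measure 17, CAMS-R 12, satisfaction 1, global impression of change 1, opioid use 1, pain catastrophizing 6 | 70 |
| Core HEAL additions, 5 × 2 | 10 |
| Self-reported utilization form | about 20 |
| **Total** | **about 100** |

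The LEC-5 (17 items, asked once at any later time point) would make it 117 if it falls at T3. The pain medication form has no stated count. The utilization form is asked monthly anyway; without it the count is 80. The Core HEAL items depend on reading the second mark in a broken table as T3; without them and the utilization form the count is 70. On any reading the PEG is a small part.

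**2. The plan's own power figure (Section 9.6)**

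Inputs: difference 1.0, SD of change 2.5, alpha 0.05 (two-sided assumed), ICC 0.053, 10 per class, 20% attrition.

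- Design effect = 1 + (10 − 1) × 0.053 = 1.477.
- The two-sample t-test needs 100, 114 and 133 per group for 80%, 85% and 90% power.
- Multiplying by 1.477 and dividing by 0.80 gives 184.6, 210.5 and 245.6. These match the plan's table to rounding.
- At 225 per arm, effective n = 225 × 0.80 / 1.477 = 121.9, and power = Φ(1 / (2.5 × √(2/121.9)) − 1.96) = Φ(1.16) = 87.8%. The t-test gives 87.5%. The plan's statement that power is near 90% is loose but consistent.

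**3. Power as T3 missingness varies**

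The documents give no T3 missingness figure, so this is an assumed range. Same formula, design effect held at 1.477.

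| Missing at T3 | Observed per arm | Effective n per arm | Power |
|---|---|---|---|
| 10% | 202.5 | 137.1 | 91.2% |
| 15% | 191.25 | 129.5 | 89.6% |
| 20% | 180 | 121.9 | 87.8% |
| 30% | 157.5 | 106.6 | 83.2% |

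Moving from 20% to 15% missing means recovering about 11 people per arm and gains about 1.8 points. If classes shrink in step with the loss, the design effect falls and the figures for 20%, 15% and 10% become 90.0%, 91.1% and 92.1%, so the gain is smaller still.

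**4. Bias, for illustration only**

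Suppose a fraction π of OPTIMUM patients is missing and these are δ PEG points worse than the model predicts, with no such departure in usual care. The bias in the T3 difference is π × δ. For δ of 1 to 2 points:

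- 20% missing: 0.20 to 0.40
- 15% missing: 0.15 to 0.30
- 10% missing: 0.10 to 0.20

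The planned difference is 1.0. The fall with π assumes that the people recovered are typical of all those missing. If those easiest to reach depart least from the model, less bias is removed, and none if their departure is zero.

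**The case against.** A reader might infer that the assessment is all-or-nothing, so that declining the long set means losing the PEG. The documents do not say so. Section 7.1 lets participants skip questions, the PEG stands first in Table 2, and a partial responder who gives the PEG enters the primary model. The electronic form's block on leaving questions unanswered (Section 10.2) works page by page and sits awkwardly with Section 7.1, but it does not turn the whole set into one unit.

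A reader might also infer that a known number of T3 outcomes could be recovered from charts. That is unsupported too. PCPs may use no scale, nothing shows that the PEG is an extractable field across two EHR platforms, and the Synopsis encourages PCP visits at the start and end of the program, not at T3. A chart score exists only if there is a visit. Visits for low back pain are themselves an EHR outcome, so availability may depend on arm and on pain.

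Further points stand. The 20% is stated for 8 weeks and as the sample-size allowance, not as a T3 forecast. The plan already targets 85% follow-up, with automated reports of missing assessments (Section 10.3.3) and weekly retention review (Section 10.3.5). Its reason for expecting more attrition is less contact with participants, not questionnaire length. Last-contact scripts could sit in procedures documents that the protocol cites but that are not available here. The missing-data plan contains no error.

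These points limit the claim but leave the gap: a target and a report of who is missing do not say what is done to obtain the primary value from those people.

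**Conclusion.** The point holds as an inexpensive improvement to data collection, not as a flaw that undermines the trial. The protocol specifies no PEG-only fallback at T3 and is silent on chart PEG scores; the number of values recoverable is unknown. Recovering 5 to 10 percentage points from an assumed 20% missing would add about 1.8 to 3.4 points of power, given the plan's SD, ICC and class size. The stronger reason is that observed values replace modelled ones for the primary contrast. The size of that benefit cannot be stated without assuming how far the missing patients depart from the model and who would respond to a short contact.

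**What to change.** Add to Section 6.2.2: anyone, in either arm, who has not completed T3 by a pre-set number of days is contacted by blinded research assistants, by telephone or short web link, for the three PEG items only. Use the same timing and number of attempts in both arms. Flag these values as PEG-only and include them in the primary mixed model. Add to Section 9.6 a sensitivity analysis that excludes them.

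The cost is a short script, one flag and one extra analysis. Staff already rescreen with the PEG alone (Section 6.2.1), the overdue reports exist, and research assistants are blinded (Section 6.2.3). The downsides are that PEG-only responders lack secondary outcomes, and that mode or timing may differ slightly from a full T3 assessment.

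Optional and exploratory: where a clinic PEG is stored as an extractable field, take the score and its date and use it as an auxiliary variable in an imputation sensitivity analysis. It should never replace the study PEG, because its availability depends on visits and may differ by arm.
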